Efficacy 	Assessment of Surgery (actual and waiting list)			X	X	X	X	X	X
	Assessment of OCS dose and duration			X	X	X	X	X	X
	Overall VAS symptom score 			X	X	X	X	X	X
	VAS symptom score for nasal obstruction, nasal discharge, mucus in the throat, loss of smell and facial pain 			X	X	X	X	X	X
	SNOT-22 			X	X	X	X	X	X
	SF-36 			X	X 	X	X	X	X
	PnIF 			X	X	X			
	UPSIT 			X	X	X			

		Pre screen 	Screening 	Treatment Phase			No treatment Follow 		
Visit		0	1	2	3 -14	15	16-17	18	EW Visit
Study day (Visit window ± 7 days)	Procedure		(28 days prior to Day 1)	1	29, 57, 85, 113, 141, 169, 197, 225, 253, 281, 309, 337	365	421, 477	533	28 days post last visit
Week				0	4, 8, 12, 16, 20, 24, 28, 32, 36, 40, 44, 48	52	60, 68	76	
	Endoscopic NP score 			X	X 	X	X	X	X
	WPAI-SHP 			X	X	X	X	X	X
	ACQ – 5 			X	X	X			X
	Asthma exacerbation			X	X	X			X
	Blood for PK 			X	X	X	X 		X
	Blood for biomarkers			X		X			
Safety	AE/SAE review			X	X	X	X	X	X
	Dispense “Medical Problems and Medication Taken Worksheet”			X	X	X	X	X	
	Collect “Medical Problems and Medication Taken Worksheet”		X	X	X	X	X	X	X
	Concurrent medication review (including INCS)			X	X	X	X	X	X
	12-lead ECG			X		X			X
	Vital signs (HR and BP)			X	X	X			X
	Laboratory assessment: Haematology			X	X	X	X	X	X
	All other Laboratory assessments (including liver chemistries)			X		X			X
	Blood for immunogenicity			X		X	X 		X
	Urinalysis			X		X			X
	Urine pregnancy test (WOCBP)			X	X	X			X
Medication/ supplies	Dispense and train on eDiary for run in and remainder of the study		X						

	Procedure	Pre screen 	Screening 	Treatment Phase			No treatment Follow 		
Visit		0	1	2	3 -14	15	16-17	18	EW Visit
Study day (Visit window $\pm$ 7 days)			(28 days prior to Day 1)	1	29, 57, 85, 113, 141, 169, 197, 225, 253, 281, 309, 337	365	421, 477	533	28 days post last visit
Week				0	4, 8, 12, 16, 20, 24, 28, 32, 36, 40, 44, 48	52	60, 68	76	
	Review and re train on eDiary (if required)			X	X	X	X	X	X
	eDiary completion 			X	X	X	X	X	X
	Review compliance and dispense MF			X	X	X 	X	X 	X 
	Dosing with study drug (active/ placebo)			X	X				
	Collect eDiary for the first 200 randomized participants							X	X

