9.1.4. Strategy for Intercurrent (Post-Randomization) Events

Only data collected while the participant was on-treatment will be used in the analysis ('while on-treatment strategy'). Blood eosinophil counts taken more than 28 days following last dose will not be included in the analysis.

Missing data will be assumed to be missing at random.

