14.4.1.1. Phases for Efficacy Assessments

Study Phase	Definition
Pre-Treatment	Assessment Date \leq Interventional Product Start Date
On-Treatment	Participants who did not withdraw early from Interventional Product: Interventional Product Start Date < Assessment Date \leq Earlier of Interventional Product Stop Date +28 days / Week 52 Visit Date Participants who withdrew early from Interventional Product: Interventional Product Start Date < Assessment Date \leq Earlier of Interventional Product Stop Date +28 days/Date of Phase Conclusion
Off-Treatment	Participants who did not withdraw early from Interventional Product: Interventional Product Stop Date +28 days < Assessment Date \leq Week 52 Visit Date Participants who withdrew early from Interventional Product: Interventional Product Stop Date + 28 days < Assessment Date \leq Date of Phase Conclusion
Off-Treatment (Follow-up after Week 52)	Participants who enter the follow-up period after Week 52: Week 52 Visit Date < Assessment Date

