14.4.1.2. Phases for Safety Assessments

Study Phase	Definition
Pre-Treatment	Assessment Date \leq Interventional Product Start Date
On-Treatment	Interventional Product Start Date < Assessment Date \leq Interventional Product Stop Date +28 days
Post -Treatment	Participants who do not enter the follow-up period after Week 52: Interventional Product Stop Date + 28 days < Assessment Date Participants who enter the follow-up period after Week 52: Interventional Product Stop Date + 28 days < Assessment Date \leq Week 52 Visit Date
Post -Treatment (Follow-up after Week 52)	Participants who enter the follow-up period after Week 52: Week 52 Visit Date < Assessment Date

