14.4.1.3. Phases for Adverse Events

Study Phase	Definition
Pre-Treatment	Event Start Date < Interventional Product Start Date
On-Treatment	Interventional Product Start Date \leq Event Start Date \leq Interventional Product Stop

CONFIDENTIAL

2020N427698_00

205687

Study Phase	Definition
	Date + 28 days
Post -Treatment	Participants who do not enter the follow-up period after Week 52: Event Start Date > Interventional Product Stop Date + 28 days Participants who enter the follow-up period after Week 52: Interventional Product Stop Date + 28 days < Event Date ≤ Week 52 Visit Date
Post -Treatment (Follow-up after Week 52)	Participants who enter the follow-up period after Week 52: Week 52 Visit Date < Event Date

NOTES: An event will be considered On-treatment if the event start date is missing and/or the interventional product stop date is missing

Where time of event is recorded, the time of event and time of first dose will be considered to differentiate between Pre-treatment and On-treatment events.

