14.5.2. Reporting Standards

General

 All data displays (Tables, Figures & Listings) will use the term “Subject” rather than “Participant” which reflects CDISC and GSK Data Display Standards terminology. Templates and standards within the current GSK Integrated Data Standards Library (IDSL) will be used for reporting unless otherwise stated. IDSL standards located at https://spope.gsk.com/sites/IDSLLibrary/SitePages/Home.aspx (under supporting documentation/component/statistical displays) will be applied: 
 4.03 to 4.24: General Principles 5.01 to 5.08: Principles Related to Data Listings 6.01 to 6.11: Principles Related to Summary Tables 7.01 to 7.13: Principles Related to Graphics
Formats

 GSK IDSL Statistical Principles for the precision to which data and summary statistics are to be presented will in general be adopted, these may be adjusted to a clinically interpretable number of decimal places (d.p.). 
 For Blood Eosinophil Counts displayed as GI/L the following will be applied: Geometric Mean, Median, Min and Max (2 d.p.); SD Logs (3 d.p.)
Planned and Actual Time

 Reporting for tables, figures and formal statistical analyses: 
 Planned time relative to dosing will be used in figures, summaries, statistical analyses and calculation of any derived parameters, unless otherwise stated. The impact of any major deviation from the planned assessment times and/or scheduled visit days on the analyses and interpretation of the results will be assessed as appropriate. Reporting for data listings: 
 Planned and actual time relative to study drug dosing will be shown in listings. Unscheduled or unplanned readings will be presented within the subject’s listings.

Unscheduled Visits	

 Unscheduled visits will not be included in summary tables and/or figures, however they will be included in listings. Data from unscheduled visits may be included in summary tables/figures when the unscheduled visit has been reassigned (Section 14.3.2). Data from unscheduled visits will be included in any-time post-baseline summaries 	
Early Withdrawal from Interventional Product or from Study	

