14.6.3. Study Population

Demographics
Age

 Year of birth is collected as ‘YYYY’ and will be presented as collected in listings Date of birth will be imputed as ‘30th June YYY’ Age is calculated according to GSK standard IDSL algorithms and is based on the imputed date of birth relative to the date of Visit 1 (Screening).
BMI

 BMI will be calculated as Weight (kg) / [Height (m)]²

Exposure
Extent of Exposure (Therapeutic Coverage)

 IP is administered approximately every 4 weeks and each dose viewed as providing therapeutic coverage for 4 weeks (28 days). Duration of exposure is calculated based on the therapeutic coverage as follows: 
 Duration of Exposure (days) = (IP Stop Date – IP Start Date + 29) Duration of Exposure (months) = (IP Stop Date – IP Start Date + 29) * 12/365.25

Exposure
Extent of Exposure (Therapeutic Coverage)

 Subject Years Exposure is calculated as follows; 
 Subject Years Exposure = $(IP\ Stop\ Date - IP\ Start\ Date + 29)/365.25$ If the IP start date is missing and there is evidence the participant received at least one dose of IP, the IP start date will be taken to be the date of randomisation, if the IP end date is missing it will be taken to be the last on-treatment visit attended. Randomised participants with no evidence of receiving at least one dose of IP will be considered as having zero days of exposure.

Exposure for treatment period and no-treatment follow-up
Number of years on and off-treatment or missing

 All participants are expected to participate in the study for at least 52 weeks (± 7 days) The number of years on-treatment will be calculated as follows: 
 $(IP\ Stop\ Date - IP\ Start\ Date + 29)/365.25$ The number of years off-treatment will be calculated as follows: 
 $Date\ of\ Phase\ Conclusion - (IP\ stop\ date + 28)/365.25$ The number of years missing will be calculated as follows for subjects who withdrew from study: 
 $1 - (number\ of\ years\ on-treatment) - (number\ of\ years\ off-treatment)$
Duration of time in no-treatment follow-up

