14.7. Appendix 7: Reporting Standards for Missing Data

14.7.1. Premature Withdrawals

Element	Reporting Detail
General	
 • The protocol objective is to collect data over the full study treatment period (up to Week 52) for all participants, whether they continue on interventional product (IP) and complete Week 52 on-treatment, or whether they withdraw prematurely from IP. 
 ○ For the participants who withdraw prematurely from IP before Week 52 and agree to the continued collection of data off-treatment, data will be collected for up to 52 weeks after randomization (or up to 76 weeks if the participant enters the Follow-up period after Week 52) either through clinic visits or via phone contact, in accordance with the participants existing visit schedule. ○ Where available, off-treatment data will be included in the analysis of the co-primary endpoints and, unless otherwise indicated, in the analysis of other efficacy endpoints. • A participant will be considered to have completed study treatment if he/she continues to take study treatment until Visit 14 (Week 48) and completes Visit 15 (week 52). • As specified in the protocol participants will be considered to have completed the study upon completion of Visit 15 (Week 52) regardless of whether they continue to take IP. • A participant eligible for the no-treatment follow-up will be considered to have completed follow-up if they continue to participate in the study until Visit 18 (Week 76) • All available data from participants who were withdrawn from the study will be listed and all available planned data will be included in summary tables and figures, unless otherwise specified. • Withdrawal visits will be slotted as per Appendix 3: Assessment Windows or will be summarised as withdrawal visits.
Pre-Screen/Screen and Run-in Failures	
 • Participants are assigned a subject number at the time of signing informed consent. • Pre-Screen Failure: A participant who is assigned a subject number but did not continue through to Visit 1. • Screening Failure: Participant performs a Visit 1 procedure, but does not enter the run-in period • Run-in Failure: Participant enters the run-in period, may perform a Visit 2 procedure, but is not subsequently randomised.

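### Safety on-treatment status ends exactly at the nominal Visit 14 to Visit 15 gap, so tables titled On-Treatment can omit a compliant completer's only scheduled post-baseline chemistry and urinalysis

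*SAP*

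**What the plan says.** All SAP references are to Amendment 1.

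- **Phase rule.** SAP 14.4.1.2 ends the safety on-treatment phase 28 days after the last dose, by assessment date. The post-treatment row reads: "Participants who do not enter the follow-up period after Week 52: Interventional Product Stop Date + 28 days < Assessment Date". Participants who enter follow-up have the same lower bound, and their post-treatment phase runs to the Week 52 visit date. Neither row mentions the visit window.
- **Basis for 28 days.** SAP 14.6.3 explains the choice: "each dose viewed as providing therapeutic coverage for 4 weeks (28 days".
- **Visit timing.** The schedule of activities (Protocol section 2) puts Visit 14 on Day 337 and Visit 15 on Day 365, each with a 7-day window either side. SAP 2.2 makes Visit 14 the last dose.
- **Laboratory schedule.** Chemistry and urinalysis are taken at Visits 2 and 15 and at early withdrawal. Haematology is taken at every treatment visit.
- **Tables.** In SAP 14.12.8, Tables 3.47-3.49 (chemistry), 3.50-3.52 (haematology) and 3.53 (urinalysis) all carry On-Treatment in their titles. No post-treatment table is listed for any of the three.
- **Default scope.** SAP 8.3 says laboratory summaries cover both on-treatment and post-treatment data unless something else is specified.
- **Exposure.** SAP 14.6.3 counts coverage in days as stop date minus start date plus 29. Table 1.21 groups the result in months, with 9 to under 12 as the next-to-top band and 12 or more as the top.

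**The concern.** A cut-off equal to the planned interval leaves no room for ordinary scheduling. A participant can take all 13 doses, attend Week 52 within the permitted window, and still have that visit classed as post-treatment because it fell a day or more late relative to the last injection.

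For most safety data this costs little. For chemistry and urinalysis it removes everything scheduled after baseline, because Visit 2 is pre-treatment and Visit 15 is the only later sample a completer is due. As titled, the change-from-baseline and shift tables would then describe a subset of completers chosen by appointment timing, and the rest would appear in no matching table. The table titles also pull against the default in SAP 8.3, and the SAP does not say which prevails.

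The same arithmetic reaches Table 1.21, where a participant treated exactly on schedule does not reach the top exposure band.

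**Working it through.** **Inputs.** Visit 14 on Day 337, Visit 15 on Day 365, window of 7 days either side (Protocol section 2; SAP 14.3.1). Cut-off of last dose + 28 days (SAP 14.4.1.2). Exposure formula (SAP 14.6.3) and bands (Table 1.21, SAP 14.12.4).

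**1. The plan's own interval.** Protocol 5.3 puts Week 52 four weeks after the last expected injection. 365 - 337 = 28 days, which reproduces it. Slack against the cut-off: 28 - 28 = 0 days.

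**2. Gaps the windows allow.**
- Shortest: Day 344 to Day 358 = 14 days.
- Longest: Day 330 to Day 372 = 42 days.
- So every gap from 29 to 42 days can occur with both visits in window, and is post-treatment by date.
- With the last dose on Day 337, the post-treatment days are 366 to 372, which is 7 of the 15 permitted Visit 15 days.
- A Week 52 visit before its nominal day can also be caught: Day 330 to Day 359 = 29 days.

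**3. What such a completer loses from the On-Treatment tables.**

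| Test | Scheduled post-baseline values | Lost | Left |
|---|---|---|---|
| Chemistry (3.47-3.49) | 1 (Visit 15) | 1 | 0 |
| Urinalysis (3.53) | 1 (Visit 15) | 1 | 0 |
| Haematology (3.50-3.52) | 13 (Visits 3-15) | 1 | 12 |

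**4. Share of completers affected.** The documents give no visit-timing data, so this cannot be computed. As an assumption only: if a fraction q of gaps is exactly 28 days and the rest split evenly either side, the affected share is (1 - q)/2. That is 0% for q = 1, 5% for q = 0.9, 15% for q = 0.7 and 25% for q = 0.5. Other assumptions give other values.

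**5. Exposure in Table 1.21.** Months = (stop date - start date + 29) x 12/365.25.
- Last dose on Day 337: 336 + 29 = 365 days; 365 x 12/365.25 = 11.99 months.
- Last dose on Day 330: 329 + 29 = 358 days, or 11.76 months.
- Last dose on Day 338: 337 + 29 = 366 days, or 12.02 months.
- So 8 of the 15 in-window last-dose days (330 to 337) fall below 12 months, including the nominal day. This needs no timing assumption.

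**The case against.** **The 28 days is deliberate.** It is the stated coverage of a dose, and the phase definitions use it throughout. SAP 14.4.1.1 even has an Off-Treatment row for people who stayed on treatment: "Participants who did not withdraw early from Interventional Product: Interventional Product Stop Date +28 days < Assessment Date". The authors therefore foresaw late Week 52 visits. This stands. A reader might infer that the cut-off is an error and should be stretched to 42 days, but the documents do not support that. It would label values beyond the stated coverage as on-treatment. It would also split laboratory data from adverse events, whose post-treatment rule is "Event Start Date > Interventional Product Stop Date + 28 days", and from the other phases that stay at 28 days.

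**SAP 8.3 already includes post-treatment data.** If it governs, nothing is lost. This stands in part. SAP 8.3 yields to anything specified otherwise, and an On-Treatment title reads as such a specification. The two need to be reconciled.

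**Nominal visits and planned time apply.** SAP 14.3.1 uses nominal visits, and SAP 14.5.2 says: "Planned time relative to dosing will be used in figures, summaries, statistical analyses and calculation of any derived parameters, unless otherwise stated". Both are general rules, and the phase definition specifically names the assessment date.

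**The eosinophil dataset.** A reader might infer that SAP 14.5.2 leaves the Week 52 eosinophil analysis ambiguous. It does not. SAP 9.1.4 is specific: "Blood eosinophil counts taken more than 28 days following last dose will not be included in the analysis". That displaces a default which applies only where nothing else is stated.

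**Little safety information is at risk.** Largely true. Liver Tables 3.54-3.55, the ALT/bilirubin plot, the ECG and vital-signs tables and Listings 47 and 50 are not labelled on-treatment and can keep late values.

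**Conclusion.** The concern holds for the scope of the laboratory tables. Read as written, the date-based rule and the table titles together remove the only scheduled post-baseline chemistry and urinalysis value of any completer seen in window 29 to 42 days after the last dose. The haematology loss is 1 of 13 visits. The conclusion rests on two readings: that phase follows the assessment date, as SAP 14.4.1.2 says, and that the titles set the scope.

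A reader might infer that many completers are affected, or that late abnormal values vanish from the report. Neither follows. The share is unknown, and late values can still reach the liver displays and, where potentially clinically important, the listings. No co-primary or ranked secondary analysis is touched. This is a reporting defect in descriptive safety tables, worth correcting because the correction is cheap.

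The Table 1.21 point is smaller and certain: an exactly on-schedule completer is shown in the 9 to under 12 month band. Table 1.22, which counts treatments administered, softens it.

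**What to change.** 1. **Laboratory tables.** State that Tables 3.47-3.53 include on-treatment and post-treatment data up to and including the Week 52 visit, in line with SAP 8.3, and remove On-Treatment from their titles. Leave all 28-day phase definitions as they are.
2. **Table 1.21.** Set the top category so that an on-schedule completer falls in it, for example at least 358 days' coverage, which corresponds to a last dose on Day 330, the earliest in-window Visit 14. Someone who missed an earlier dose but was dosed at Visit 14 would also qualify, so read it beside Table 1.22.
3. **Optional.** Add a supportive eosinophil repeated-measures model that keeps all Week 52 counts from participants dosed at Visit 14. The main analysis under SAP 9.1.4 stays unchanged.

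**Cost.** Items 1 and 2 need SAP wording, seven table titles with their data selection, and one category limit; item 3 adds one model run. The downside of item 1 is that some values more than 28 days after the last dose enter these tables. For participants who stopped treatment early but stayed in the study, the interval can be much longer than 42 days. SAP 14.5.1 already requires analysis datasets to flag whether each observation was made on or after randomised treatment, so such values can be footnoted or counted separately.

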14.4.1.3. Phases for Adverse Events

Study Phase	Definition
Pre-Treatment	Event Start Date < Interventional Product Start Date
On-Treatment	Interventional Product Start Date \leq Event Start Date \leq Interventional Product Stop

CONFIDENTIAL

2020N427698_00

205687

Study Phase	Definition
	Date + 28 days
Post -Treatment	Participants who do not enter the follow-up period after Week 52: Event Start Date > Interventional Product Stop Date + 28 days Participants who enter the follow-up period after Week 52: Interventional Product Stop Date + 28 days < Event Date ≤ Week 52 Visit Date
Post -Treatment (Follow-up after Week 52)	Participants who enter the follow-up period after Week 52: Week 52 Visit Date < Event Date

NOTES: An event will be considered On-treatment if the event start date is missing and/or the interventional product stop date is missing

Where time of event is recorded, the time of event and time of first dose will be considered to differentiate between Pre-treatment and On-treatment events.

14.4.1.4. Phases for Concomitant Medication Start Dates

Study Phase	Definition
Pre-Treatment (Started prior to treatment)	Concomitant medication (CM) start date < IP start date
On-Treatment (Started during Treatment)	If CM start date is on/after IP start date & on/before IP stop date +28 days. (IP Start Date ≤ CM Start Date ≤ IP Stop Date + 28 days)
Post-Treatment (Started post- treatment)	If CM start date is after the IP stop date + 28 days. (CM Start Date > IP Stop Date + 28 days)
Follow-Up After Week 52 (started during the Follow- up period after Week 52)	Participants who enter the follow-up period after Week 52: If CM start date is after the Week 52 Visit date.

NOTES: If the IP stop date is missing and/or the CM start date is missing then the CM is considered to have started on-treatment

14.4.1.5. Phases for Concomitant Medication Usage Dates

Study Phase	Definition
Taken Prior to Treatment	If CM start date < IP Start Date
Taken During Treatment	If CM start date < IP start date and CM stop date ≥ IP start date If IP start date < CM start Date ≤ IP Stop Date + 28 days
Taken Post-Treatment	If CM start date ≤ IP stop date+28 days and CM stop date > IP stop date +28 days If CM start Date > IP stop date + 28 days

NOTES: If the IP stop date is missing and CM start date is on/after IP start date then CM considered taken during treatment

If CM start date is missing, then CM considered to be taken during treatment

14.5. Appendix 5: Data Display Standards & Handling Conventions

14.5.1. Reporting Process

Software	

 The currently supported versions of SAS software will be used. 	
Reporting Area	
HARP Server	PPD
HARP Compound	
Analysis Datasets	

 Analysis datasets will be created according to CDISC standards [SDTM IG Version 3.2 & ADaM IG Version 1.1]. Analysis datasets will include variables to clearly indicate whether each observation was observed while the patient was on randomized treatment, observed after the patient discontinued randomized treatment, or was imputed or is missing. 	
Generation of RTF Files	

 RTF files will be generated for the final reporting effort. 	

14.5.2. Reporting Standards

General

 All data displays (Tables, Figures & Listings) will use the term “Subject” rather than “Participant” which reflects CDISC and GSK Data Display Standards terminology. Templates and standards within the current GSK Integrated Data Standards Library (IDSL) will be used for reporting unless otherwise stated. IDSL standards located at https://spope.gsk.com/sites/IDSLLibrary/SitePages/Home.aspx (under supporting documentation/component/statistical displays) will be applied: 
 4.03 to 4.24: General Principles 5.01 to 5.08: Principles Related to Data Listings 6.01 to 6.11: Principles Related to Summary Tables 7.01 to 7.13: Principles Related to Graphics
Formats

 GSK IDSL Statistical Principles for the precision to which data and summary statistics are to be presented will in general be adopted, these may be adjusted to a clinically interpretable number of decimal places (d.p.). 
 For Blood Eosinophil Counts displayed as GI/L the following will be applied: Geometric Mean, Median, Min and Max (2 d.p.); SD Logs (3 d.p.)
Planned and Actual Time

 Reporting for tables, figures and formal statistical analyses: 
 Planned time relative to dosing will be used in figures, summaries, statistical analyses and calculation of any derived parameters, unless otherwise stated. The impact of any major deviation from the planned assessment times and/or scheduled visit days on the analyses and interpretation of the results will be assessed as appropriate. Reporting for data listings: 
 Planned and actual time relative to study drug dosing will be shown in listings. Unscheduled or unplanned readings will be presented within the subject’s listings.

Unscheduled Visits	

 Unscheduled visits will not be included in summary tables and/or figures, however they will be included in listings. Data from unscheduled visits may be included in summary tables/figures when the unscheduled visit has been reassigned (Section 14.3.2). Data from unscheduled visits will be included in any-time post-baseline summaries 	
Early Withdrawal from Interventional Product or from Study	

 Data recorded at the early withdrawal visit will be re-assigned to the next scheduled visit, unless information already exists at that visit. Early withdrawal data re-assigned to a scheduled visit will be included in analyses, summary tables and figures by scheduled visit. Early withdrawal visit data that is not re-assigned to a scheduled visit will not be included in analyses, summary tables or figures by scheduled visit. Data recorded at early withdrawal visits will be included in the assessment of maximum or worst-case post-baseline for relevant endpoints. Data from all early withdrawal visits will be included in listings. 	
Descriptive Summary Statistics	
Continuous Data	n, mean, standard deviation or standard error, median, minimum, maximum
Categorical Data	N, n, frequency, %
Graphical Displays	

 Refer to IDSL Statistical Principals for Graphics 	

